Data collection will be conducted at the Northampton VA Medical Center and the West Haven VA Medical Center. Veterans will complete baseline evaluations, and then be given a user ID and instructions to log-on to a study website at home to receive their randomization assignment. Only those who do so will continue in the study and be asked to complete the telephone-delivered assessments on weeks 4, 12, and 24. This randomization after logging in restricts participation to people who demonstrate some motivation and ability to access a website.

Sequence of procedures for the clinical trial:

- Potentially eligible Veterans scheduled for a Compensation examination are identified by reviewing Compensation clinic schedules and charts.
- Potentially eligible Veteran receives letter explaining that a study recruitment telephone call will be coming, thus allowing the Veteran to opt out of receiving it (see Appendix). Veterans can also opt out by calling a toll-free phone provided in the letter.
- Telephone call inviting participation. The Research Assistant calls and asks the Veteran questions to determine eligibility. Following a script (see Appendix), the Research Assistant describes the study to the Veteran and schedules an appointment for informed consent and data collection. Appointments will be scheduled before a Veteran's planned Compensation examination and up to 3 months after the exam. Veterans vary in how able they are to schedule appointments immediately before or after Compensation examinations. Flexible scheduling balances feasibility and experimental rigor.
- Informed consent and baseline data collection by Research Assistant.
- The Research Assistant gives the Veteran a user ID and password to log on to the study Website.
- Veteran goes home, logs onto the website, and receives directions to log-on to either the Benefits Counseling or Control websites (i.e. the Veteran is randomized).
- Veteran is called by the study therapist within two days of logging on and is counseled with the assigned treatment. If the Veteran has not logged on for randomization within a week, then the therapist will call and encourage the Veteran to log-on for randomization and continuation in the study. If after one more week the Veteran has not been randomized, that participant will be discontinued from the study.
- Assessments by phone at weeks 4, 12, 24 (only of randomized Veterans).

B. Remotely-Delivered Benefits Counseling

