- b. The VBA site with fact sheets about the different types of benefits available to Veterans. The topics covered in these fact sheets are: General Benefit Information, Veterans with Service-Connected Disabilities, Veterans with Limited Income, Education and Training for Veterans, Home Loans, Dependents and Survivors' Benefits, Burial and Memorial Benefits, and Insurance.
- c. The VBA websites for the local C&P office where issues pertaining to an individual Veteran's specific application are addressed. The site includes phone numbers to call with questions, e-mail contacts and directions to the VBA office.

3. Role of Therapists in Control Condition: The therapists in the control condition will differ from the Benefits Counseling therapist as shown in the table below

Control Therapist	Benefits Counseling Therapist
Initiate calls to Veterans at weeks 1 and 2	Initiate calls to Veteran at weeks 1 and 2 and around time of Module Three (or thereafter)
Up to three therapy calls of up to 30 minutes each	Up to three therapy calls of up to 30 minutes each
Convey information about Veterans Benefits	Convey information about Veterans Benefits AND vocational issues
Offer to elaborate on information on control websites	Inquiry about modules on Benefits Counseling website. Follow-up inquiries about domains covered on site.

Justification of Sample Size

We estimate that 190 Veterans will be enrolled and complete baseline assessments; 130 will log-in to the randomization site and be assigned to a treatment condition; 104 (52 per condition) will complete at least one follow-up assessment.

Precision Analysis

Consistent with the purpose of a pilot study, the sample size was selected to

estimate the standardized effect of treatment with reasonable precision, rather than to power for a statistically significant effect [50]; A **sample size of 52 per treatment condition** permits estimation of an expected standardized difference in slopes of hours worked between Benefits Counseling and control groups (e.g., (slopeBC-slopeCON)/SDslope) of $\delta=.40$ with a 95% confidence interval of (.01, .79). This effect would reflect an average 6% increase in baseline number of hours worked per month, or a total increase of 43% by month 6. Assuming an average baseline event rate of 40 hours/28 days and no change in the control group, this effect is equivalent to approximately 17 additional hours (approximately 2 days) of work per month by month 6.

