We planned our precision analysis around an effect size of 0.4 because (a) the effect size in our RCT of face-to-face Benefits Counseling was $\delta=.69$ and (b) an effect size of 0.4 is clinically meaningful. An additional 2 days worked reflects earning a substantial amount of additional money for people with limited incomes, in addition to other benefits associated with working.

D. Experimental Participants

1. Inclusion and Exclusion Criteria

a. *Inclusion Criteria*: All enrolled participants will have difficulty working as evidenced by a “Yes” response to any sub-part of the question below (from the SF-36, [51]): “During the past 4 weeks, have you had any of the following problems with your work or other regular daily activities as a result of any emotional problems (such as feeling depressed or anxious): (a) Cut down on the amount of time you spent on work or other activities? (b) Accomplished less than you would like? (c) Didn’t do work or other activities as carefully as usual?”

Participants will also meet the following inclusion criteria: (i) A Compensation and Pension evaluation by a psychiatrist or psychologist is scheduled; (ii) Does not have a service-connected physical disability rated over 30%; (iii) Is not service-connected for a psychiatric condition (0% service-connection is allowed, as Veterans with 0% service-connection have not received any benefit payments); (iv) Age 18-65; (v) Reports access to an internet-connected computer/tablet and a working telephone; (vi) Reports working no more than 24 hours per week for pay over the preceding 4 weeks; (vii) Self-reported ability to participate psychologically and physically, able to give informed consent and complete assessments; (viii) Reports being able to read (this is necessary for understanding the website); (ix) Expressed interest in sampling whatever website is provided.

b. *Exclusion Criteria*: (i) Already receiving service-connection, SSI or SSDI; (ii) Has a conservator.

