2. *Feasibility of Randomizing 130 Veterans*: A review of Compensation examinations conducted at Northampton over a 12 month period showed that 547 were conducted for psychiatric conditions. Of these, 348 were initial examinations, 190 were reviews, and 9 were for other reasons. We are estimating that approximately 60% of the 348 will be working fewer than two days per week and receiving less than 30% service-connection. In a chart review of Compensation examinations conducted at our MIRECC site in Bedford, approximately half (17 out of 38) of Veterans coming for new psychiatric Compensation evaluations were both not working *at all* and less than 30% service-connected. Some Veterans will be excluded for other reasons. Therefore, we estimate that 209 eligible Veterans will be approached in a year, which is enough to randomize 130 over two and a half years of recruitment.

3. Balancing the study groups: Participants will be randomized by the Project Director, with assignment delivered by the website, using an urn randomization procedure [52] that offers the benefits of balancing allocation of important prognostic variables in treatment groups, while still retaining other benefits of random assignment. The factors in the urn will be those potentially related to vocational outcomes in Veterans:

- Self-reported use of an illicit drug and/or risky alcohol use within the past 3 months (as measured by the ASSIST, using standard definitions [53,60,61,62]) within the last 28 days. Opioid use will qualify if the opioids were *not* prescribed to the Veteran.
- Current enrollment in VA psychiatric or substance abuse treatment (yes/no).
- Race (African American –yes/no) has been associated with responses to remotely-delivered behavioral messages [54].

Justification for Why Follow-up Data Collection after Baseline will be Done via Telephone:

Timeline followbacks have been administered by phone for substance abuse evaluation and are highly consistent with face-to- face assessments conducted in the same participants---in fact reports of substance use were numerically higher with the telephone assessment, suggesting a greater likelihood of truthful reporting of embarrassing information by phone [55]. The follow-up assessments are also relatively brief, taking 30 minutes or less per session. Veterans will have already completed these assessments at the face-to-face baseline visit so they will be familiar with them when they are re-administered by phone.

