1. Determination of Study Outcomes: We list below the outcome measures whose scoring requires explication. Many of the scales' scoring is embedded in our earlier description of the measure.

a. Primary Outcome: The a priori definition of a primary outcome reduces the risk of Type I error. The number of hours paid work will be the primary treatment outcome. As noted previously, this includes work that is formal or under-the-table, and includes formal in-kind arrangements. It does not include days engaged in informal in-kind arrangements (housekeeping) or illegal activities such as gambling.

b. Secondary Outcomes: Secondary outcomes include each of the other work-related activities considered separately (unpaid work, attending school, engaging in vocational rehabilitation). Another secondary outcome is days engaged in any of the above work-related activities. This measure of work-related activities has a range of 0 to 28 in that each day is scored for whether any work-related activity was engaged in on that day as a dichotomous (0,1) value.

Dollars earned will be log-transformed (adding “1” to totals before transformation to allow calculation for veterans with no income) for outcome analyses if it is heavily skewed by outliers with high incomes.

c. Scoring of Clinical Measures.

- i. Psychiatric Symptomatology: The Global Severity Index from the Brief Symptom Inventory will be the main outcome from the BSI. The depression subscale will be scored too because of the association between depression and poor work function.
- ii. The SF-36 will be scored to yield standardized Mental Health and Physical Health Component Scores, with a mean of 50 and population standard deviation of 10. As noted earlier, the PTSD Checklist items are summed to yield a single score.
- iii. For the Work-Related Attitudes Scale, EFA will be conducted if it can be accomplished with the sample, i.e., if there is approximately a 10:1 participant:item ratio and item communalities are high [.6 or greater] after dropping any items with poor variability. If EFA is not feasible, we will analyze inter-item correlations and estimate internal consistency reliabilities to identify items that cluster together within a domain that reflect the perceived work-benefits relationship. A mean score of all items in this domain (or domains, if more than one is identified), will be generated.
- iv. The ASSIST yields an overall substance use severity score.

d. Process Measures

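### Is the unsourced baseline of 40 paid hours per 28 days, and hence the 2 extra days of work equated with an effect of 0.40, at odds with the plan's own feasibility figures?

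*Combined protocol and SAP*

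**What the plan says.** The Precision Analysis, under Justification of Sample Size, plans for 52 Veterans per arm so that a standardized slope difference of 0.40 has a 95% confidence interval of (.01, .79). It equates 0.40 with "an average 6% increase in baseline number of hours worked per month, or a total increase of 43% by month 6". It then converts this to about 17 hours, or about 2 days, of extra work per month by month 6, "Assuming an average baseline event rate of 40 hours/28 days and no change in the control group".

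Two reasons are given for planning around 0.40: the effect of 0.69 in the earlier face-to-face trial, and the claim that 0.40 is clinically meaningful. The second reason is supported by the statement that "An additional 2 days worked reflects earning a substantial amount of additional money for people with limited incomes", along with other benefits of working.

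Other sections bear on the baseline:

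- Inclusion criterion (vi): "Reports working no more than 24 hours per week for pay over the preceding 4 weeks".
- Feasibility of Randomizing 130 Veterans, for Northampton: an estimate that "approximately 60% of the 348 will be working fewer than two days per week and receiving less than 30% service-connection". From this the plan counts 209 eligible Veterans a year.
- The same section, for Bedford: a chart review in which "approximately half (17 out of 38) of Veterans coming for new psychiatric Compensation evaluations were both not working" at all and under 30% service-connected.
- Study Design Overview: "Data collection will be conducted at the Northampton VA Medical Center and the West Haven VA Medical Center".
- Data Analysis, Primary Outcome, on paid work: "this includes work that is formal or under-the-table".

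**The concern.** The 40 hours is a mean over everyone, non-workers included, and has no citation or derivation. The earlier trial contributes only an effect size, and that was for days worked. The feasibility section, meanwhile, describes a pool in which many Veterans do no paid work. If most participants start at zero and the rest are capped, a mean of 10 hours per week looks high.

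The stake is interpretation. If the effect is a percentage rise, the extra hours shrink in proportion to the baseline. The 2 days is the main support for calling 0.40 clinically meaningful, so readers might judge the interval (.01, .79) against too generous a benchmark.

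**Working it through.** **The plan's own figures reproduce.**

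- Growth: exp(6 × 0.06) = 1.433, which matches 43%. Simple addition gives 6 × 6% = 36%, and monthly compounding gives 1.06^6 − 1 = 41.9%. The 43% therefore fits a slope on the log-rate scale.
- Hours: 0.43 × 40 = 17.2, and 17.2 / 8 = 2.15 eight-hour days.
- Interval: 0.40 ± 1.96 × √(2/52 + 0.40²/208) = 0.40 ± 0.388 = (.012, .788), which rounds to (.01, .79). Baseline hours do not enter this formula.

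**The apparent conflict.** Inputs are 17/38 and 60% (feasibility section) and 24 hours per week, or 96 hours per 28 days (criterion vi). Eight-hour days are assumed, so two days per week is 64 hours per 28 days.

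- Not working: 17/38 = 0.447. As a share of the 60% pool: 0.447 / 0.60 = 0.746. Working: 0.254.
- Largest mean if every worker is at the 96-hour cap: 0.254 × 96 = 24.4 hours. Gain: 0.43 × 24.4 = 10.5 hours (1.3 days).
- Largest mean if every worker is at 64 hours: 0.254 × 64 = 16.3 hours. Gain: 0.43 × 16.3 = 7.0 hours (0.9 day).

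**How firm those ceilings are.**

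- *Sampling error.* The Wilson 95% interval for 17/38 is 0.301 to 0.603. At the lower limit the non-working share is 0.301 / 0.60 = 0.502, and the 96-hour ceiling is 0.498 × 96 = 47.8 hours. A 40-hour mean then needs workers to average 40 / 0.498 = 80.4 hours, or 20.1 hours per week, which criterion (vi) allows. At the upper limit, 0.603 / 0.60 exceeds 1, which no share can do, so the quotient is fragile.
- *Mixed definitions.* The 60% is defined by fewer than two days per week. On eight-hour days criterion (vi) is looser, so it admits more workers and lowers the non-working share. The 24.4 hours takes the looser cap but keeps the narrower pool, so it is not an upper bound for the population enrolled. With 70% eligible, the ceiling is (1 − 0.447/0.70) × 96 = 34.6 hours and the gain 14.9 hours (1.9 days). With 17/38 held fixed, 40 hours becomes reachable once 0.447 / (1 − 40/96) = 77% are eligible, with every worker at the cap. If all 38 Bedford Veterans were eligible, workers would need 40 / 0.553 = 72.4 hours, or 18.1 per week.
- *Different sites and measures.* Bedford is not one of the two data-collection sites. A chart entry of not working may also miss under-the-table work, which the outcome counts.
- *Scale.* Proportional shrinkage needs a fixed standard deviation of the log slope (implied value 0.06 / 0.40 = 0.15 per month). The plan states neither the standard deviation nor its scale. If the standard deviation is fixed in hours, 0.40 is the same number of hours at any baseline.

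**The case for a change.** The strongest case for the concern is that the plan itself sets the two feasibility figures side by side. Both describe new psychiatric examinations, both use the 30% service-connection limit, and the plan counts the 60% pool as its eligible Veterans (0.60 × 348 = 209). Dividing one by the other is a natural reading. The ceilings also put every worker at the limit. Under the two-days wording, the ceiling stays below 40 hours even at the lower limit for 17/38 (0.498 × 64 = 31.8 hours) or with all 38 eligible (0.553 × 64 = 35.4 hours). A gain of two eight-hour days needs a baseline of at least 16 / 0.43 = 37.2 hours.

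Part of this stands. The 40 hours is unsourced, the work limits in criterion (vi) and the feasibility section differ, and a 40-hour mean requires fairly high hours among those who work. But entry is governed by criterion (vi), and the two-days wording only describes a rough recruitment estimate. Under criterion (vi), 40 hours lies within the uncertainty of the plan's own figures.

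**Conclusion.** The concern identifies missing detail, not an error. At the point figures the mean baseline would be nearer 16 to 24 hours than 40. That result rests on a quotient of two loosely related numbers, on eight-hour days and, for the smaller gain, on a log-scale slope with unchanged spread. It is indicative only and does not establish that 40 hours is too high.

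Nothing in the design depends on it. The trial is sized for precision, and no power calculation, decision threshold or analysis uses the 17 hours or the 2 days. The earlier effect of 0.69 is a separate reason for planning around 0.40. The documents set no minimum worthwhile number of hours, so a smaller equivalent would not by itself make 0.40 unimportant.

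The gap also closes when results are reported. Paid work is recorded on the timeline follow-back calendar at baseline, so analysts can restate a fitted ratio in hours from the observed mean. For a 43% rise, 20 hours gives 8.6, 30 gives 12.9 and 40 gives 17.2. Citing a source for the 40 hours would be a courtesy to readers. The 52 per arm, the 0.40, the interval and the analysis would stay as they are, so no change is called for.

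### The urn leaves out baseline paid work, the starting value of the primary outcome, and no fixed covariate in the model makes up for it: a cheap gain in balance and precision is missed

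*Combined protocol and SAP*

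**What the plan says.** **Eligibility.** Inclusion criterion (vi) reads: "Reports working no more than 24 hours per week for pay over the preceding 4 weeks". There is no minimum, so the range is 0 to 24 × 4 = 96 hours per 28 days. Under Feasibility of Randomizing 130 Veterans, 17 of 38 new examinees at another site "were both not working *at all* and less than 30% service-connected", so a mix of workers and non-workers is expected.

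**Allocation.** Balancing the study groups introduces the urn with "The factors in the urn will be those potentially related to vocational outcomes in Veterans". It then names three: illicit drug or risky alcohol use, current VA psychiatric or substance abuse treatment, and African American race.

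**Timing.** The Study Design Overview puts baseline data collection before the Veteran logs on and is assigned. The Schedule of Assessments includes the timeline follow-back calendar of paid work at baseline.

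**Size.** The Justification of Sample Size states that "130 will log-in to the randomization site and be assigned to a treatment condition" and "104 (52 per condition) will complete at least one follow-up assessment". The Precision Analysis chose the number to estimate an effect "rather than to power for a statistically significant effect".

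**Analysis.** The primary outcome is hours of paid work, compared as slopes by random effects regression on all randomized Veterans. Evaluation of Treatment Effects provides for baseline tests between arms; a variable that differs and is related to outcome becomes a covariate. It also refers to covariates described in an Introduction Section. The supplied text contains no such list.

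**The concern.** How paid hours change over six months plausibly depends on where a Veteran starts. Someone at zero can only stay there or rise, while someone near the 96-hour ceiling has room to fall. Under a Poisson model, which the plan allows, change is proportional to the starting level. Using baseline as the first repeated measure absorbs a difference in level between arms, but not a dependence of slope on level.

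Among factors related to vocational outcome, recent paid work is the most direct. It is available in time for the urn and needs no new data. Without it, the two arms of a small trial can differ noticeably in the share already working, and the slope contrast carries that noise. The test-triggered adjustment acts only on large gaps. What is at stake is precision, and the credibility of the one allocation that the trial will realise.

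**Working it through.** **1. The plan's own interval.** With d = 0.40 and 52 per arm, SE = √(2/52 + 0.40²/(4 × 52)) = 0.198, and 0.40 ± 1.96 × 0.198 = (0.012, 0.788). This reproduces the stated (.01, .79). Also 104/130 = 0.80, so 20% without follow-up is assumed.

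**2. Share working at baseline (assumed).** I use 25% to 55%. The documents do not give the share, but 17/38 = 45% not working corresponds to 55% working. Setting that 45% against the 60% expected to be eligible gives about 75% not working, hence 25% working. This second figure mixes two sites and two rules, so it is indicative only.

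**3. Chance of a gap with work left out of the urn.** The documents imply 1:1 allocation but do not state it. The hypergeometric distribution for 130 split 65/65 gives:

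| Number working of 130 | Share | SD of gap | P(gap ≥ 10 points) |
|---|---|---|---|
| 32 | 25% | 0.076 | 15% |
| 33 | 25% | 0.077 | 23% |
| 52 | 40% | 0.086 | 21% |
| 65 | 50% | 0.088 | 29% |
| 72 | 55% | 0.088 | 22% |

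The jumps come from discreteness. The range is about 15% to 29%. Among the 104 with follow-up, the SD of the gap is 0.085 to 0.098.

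**4. When the baseline test would act.** The plan gives no significance level. Assuming 5% and 65 per arm, a gap in the share working reaches significance at about 1.96 × √(2 × 0.25/65) = 0.17 if half work, or 1.96 × √(2 × 0.1875/65) = 0.15 if a quarter work. For hours, the threshold is about 0.35 SD. Gaps of 10 to 15 points would usually go unadjusted.

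**5. Share of the contrast's variance.** The Precision Analysis equates 0.40 with about 17 hours, so one SD is 17/0.40 = 42.5 hours and the SE is 42.5 × 0.198 = 8.4 hours. Assume workers and non-workers differ by 20 to 40 hours in natural six-month change; the documents give no figure. With 52 per arm, to match the stated interval, the SD from imbalance is 0.085 × 20 = 1.7 hours to 0.098 × 40 = 3.9 hours.

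- (1.7/8.4)² = 0.04
- (3.9/8.42)² = 0.21

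This is a component of the 8.4 hours, not an addition to it. Removing all of it would take the half-width from 0.39 to 0.388 × √(1 − 0.04) = 0.38 or 0.388 × √(1 − 0.21) = 0.34.

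**6. Effect of a fourth urn factor.** I simulated 130 assignments with one urn per factor, each starting with one ball per arm, and drew from the most unbalanced urn. Assumed prevalences of the existing factors are 30%, 40% and 12%, independent of work status.

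| Share working | P(gap ≥ 10 points), three factors | With work added | SD of gap, three factors | With work added |
|---|---|---|---|---|
| 50% | 27% | 11% | 0.089 | 0.062 |
| 25% | 18% | 4% | 0.075 | 0.052 |

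A repeat with another random seed gave 6% in place of 4%. The variance remaining is (0.062/0.089)² = 0.49 and (0.052/0.075)² = 0.48, so about half is removed.

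**The case against.** The strongest reply is that this is ordinary sampling error. Randomisation keeps the comparison unbiased on average, and variation in slope due to starting status is already inside the slope SD behind the (.01, .79) interval. The plan also has a route to adjustment, and baseline work may be on the covariate list that the text does not contain. The protocol promises factors related to vocational outcomes, not every such factor or the strongest. It describes itself as a pilot sized for precision. All of this stands, and it limits the point to lost efficiency.

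It does not dispose of the point. An interval that allows for avoidable noise is wider than it need be, and precision is this trial's declared purpose. The test-triggered route would miss moderate gaps.

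A reader might go further and infer that chance imbalance would drive the arms' slopes apart as a systematic distortion, or that the primary outcome's baseline is wholly uncontrolled. The documents support neither. The first confuses variance with bias. The second is true of allocation but only partly of analysis, because the model uses baseline as a repeated measure and conditional adjustment is provided for. Nor would a yes/no urn factor remove most of the imbalance: about half remains, and hours among workers stay unbalanced.

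**Conclusion.** The point holds as a cheap improvement of moderate to low severity. Baseline paid work is absent from the urn although it is known before assignment, and nothing in the supplied text makes it a fixed covariate. The type I error rate and the unbiasedness of the randomised comparison are unaffected.

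The 15% to 29% chance of a gap rests on the assumed share working and on equal arms. The 4% to 21% of variance rests in addition on the assumed 20 to 40 hour difference in natural change, for which the documents offer no figure. If that difference is smaller, so is the gain.

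**What to change.** 1. Add a fourth urn factor: any paid work in the 28 days before baseline (yes/no), taken from the timeline follow-back.
2. Prespecify that factor and its interaction with time in the primary slope model, regardless of any baseline test. Balance alone would not narrow the reported interval; the model terms let it reflect the gain. They also help for Veterans already randomized under the three-factor urn.
3. List the model's covariates in the analysis section itself, in place of the reference to an Introduction Section.

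The cost is one more binary input at randomization, slightly looser balance on the three existing factors, and one or two more model terms. No new data are collected and the sample size does not change.
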